The purpose of this study is to evaluate the efficacy of using the Arthroflex (A-FLEX) graft to augment large to massive arthroscopic rotator cuff repairs *in vivo* and decrease repair failures in a prospective, randomized, controlled trial. By undergoing serial US examinations at follow-ups, we also intend to evaluate when during the postoperative period the failure of the repair occurs.

1. Study Design

Methods

This is a prospective, randomized, controlled, multi-center clinical trial to evaluate the effectiveness of an ECM scaffold graft to augment repair of a large/massive rotator cuff tear. The study will involve 70 patients. 35 patients will be randomly assigned to each arm of the study.

A-FLEX graft will be used in those patients randomly assigned to the treatment group who are undergoing an arthroscopic large (defined as 2.5-5 cm) or massive (defined as >5 cm) rotator cuff repair. Patients randomly assigned into the control group will undergo open or arthroscopic rotator cuff repair using the surgeon's standard technique.

A. Inclusion Criteria

The following patients will be found eligible for inclusion into the study sample:

1. Patients with a large (2.5-5 cm) to massive (>5 cm) rotator cuff tear who will be undergoing open or arthroscopic repair. The cuff tear size will be determined on either pre-operative magnetic resonance imaging (MRI), or ultrasound (US), or intra-operative measurements, or computerized tomography (CT).
2. Patients who are willing and able to provide written informed consent for their involvement in the study.
3. Patients who meet criteria for RCR surgery.
4. Patients older than 18 years of age.

B. Exclusion Criteria

The following patients will not be found eligible for inclusion into the study sample.

1. Those with a known sensitivity to materials of porcine origin.
2. Patients with addiction to illegal drugs, solvents or alcohol who are actively using or have previously attempted and failed a treatment program.
3. Patients with bacteremia, a systemic infection, or infection of the surgical site.
4. All those who are prisoners.
5. Patients who are pregnant or nursing.
6. All those with a condition that may limit a patient's ability to finalize the study or that may cause an undue risk to the patient's health and well-being.

2. Research Procedures

Treatment Plan

A. Preoperative Screening

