Patients scheduled for an open or arthroscopic repair of a rotator cuff tear ≥ 2.5 cm will be identified during clinical visits or through EPIC. If the patient meets the eligibility inclusion/exclusion criteria for the study, he or she will be asked to participate in the study the following way:

During a patient's pre-operative clinical visit, the researcher will describe in detail the study at hand including, but not limited to, study benefits, potential risks, and alternative treatment modalities. He/she will hand a copy of the Informed Consent to the patient for review. If the patient agrees to participate in the study, the written informed consent will be completed and filed. The patient will be told explicitly that if he or she declines participation, his or her care will not be affected.

If patient is unavailable during pre-operative clinical visit, patient will be contacted via phone call. Any information regarding the study including IRB approved consent and brochure will be emailed and/or mailed to the patient for review. There will be documentation in the patient's chart when this patient was contacted via phone. Patient will be consented in-person on same-day as surgery, only if the above is completed and documented.

B. Enrolled Patients

After enrollment, all indicated preoperative assessments will be performed and recorded.

C. Randomization

All patients that meet the criteria will be randomized the day the informed consent is signed. If the patient is randomized into the control group, the surgery will continue as planned with no ECM scaffold graft to augment the repair. However, if the patient falls within the treatment group, an FDA-approved ECM scaffold graft will be used to augment the repair. The post-operative care will be as per standard care following a rotator cuff repair. There is no expectation that the patient should require a longer hospital stay.

D. Surgical Treatment

All surgical procedures will be performed by Board Certified and Fellowship trained Orthopedic Surgeons from Cleveland Clinic, [name] or as appointed by the PI. A standardized surgical repair technique will be used by the participating surgeon.

1. Control Treatment Group

Patients randomly assigned into the control group will undergo open or arthroscopic rotator cuff repair using the surgeon's standard practice. No ECM graft will be used.

2. Treatment Group

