Patients randomly assigned into the treatment group will undergo open or arthroscopic rotator cuff repair with A-FLEX graft to augment the repair. ECM scaffold grafts are indicated for the reinforcement of soft tissues repaired by sutures or suture anchors during tendon repair surgery, including rotator cuff.

3. Alternative Treatment Group

Patients who meet pre-op inclusion criteria where a repair cannot be accomplished due to intraoperative findings will remain in the study. This group will be analyzed separately and still follow study procedures.

E. Surgical Methods

Prior to repair

Tendon qualities and measurements will quantified and recorded:

- Tear size, retraction, quality of tissue

Arthroscopic Primary Rotator Cuff Repair

All patients will undergo arthroscopic primary repair using a suture bridge technique. An acromioplasty, distal clavicle excision and biceps tenodesis or tenotomy may be performed by routine techniques as clinically indicated. The tendon tear will be identified and mobilized, as indicated, such that the tendon can be approximated over the greater tuberosity. Standard double row suture bridge fixation technique will be used for all repairs

Mini-open/ Arthroscopic Graft Augmentation

In patients receiving a graft, thru mini open technique the lateral portal incision will be extended vertically approximately 5-6 cm. A standard, deltoid-splitting, mini-open approach will then be performed, leaving the deltoid attachment to the acromion intact. For arthroscopic technique same method of fixation will be used below. The dermis graft will be sized and cut so as to cover the entire repair site in both medial-lateral and anterior-posterior dimensions. The medial sutures previously placed in the tendon at the time of arthroscopic repair will then be passed in a mattress technique through the medial side of the graft. At least two

mattress sutures will be used, bringing the graft medial to the medial sutures used for the primary tendon repair. The graft will then be tensioned and secured in the anterior-posterior direction using at least two sutures on each side, passed through intact rotator cuff tissue. The suture limbs retained from the laterally placed suture bridge repair anchors will be placed as mattress sutures into the graft, and the graft will be tensioned to a position distal to the repair footprint.

Data for RCR will be recorded:

- Number of anchors
- Quality of repair
- Footprint coverage

3. Assessments

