Approximately 70 subjects are needed to assess the primary outcome, measured as the percentage of repairs that heal and remain intact after 1 year. A re-tear rate of 40% is expected in patients who have undergone rotator cuff repair for large and massive rotator cuff tears, based on the current literature (reference ted below). We anticipate that in this study, the percentage of re-tears in the augmented group will be reduced by

approximately half (~20%), while the control group would experience rates of re-tear comparable to what is reported in the current literature (~40%). Reducing this rate by half would be clinically meaningful. An SD of 15% within groups was allowed. Power analysis indicated that 20 patients in each group would provide sufficient power to identify statistical significance in healing rates between the control and augmented groups. With the assumption that the control group will have a failure rate of approximately 40% and the augmented group will have a failure rate of approximately 20%, at least 34 should be randomized in the control group and 26 in the augmented group. It is estimated that an overall fewer percentage of subjects initially randomized to the control group will complete the trial as augmentation may be required due to tear severity and other procedure variables. Those patients randomized to the control arm and withdrawn for repair by augmentation may be followed for safety.

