notified. The situation will be discussed among surgical faculty, and if there is a prudent solution, it will be presented to the IRB for approval. If there are no effective solutions, the investigators will have no choice but to discontinue the study.

Data will be reviewed by the PI and physicians conducting the study. The ECM scaffold grafts have not been linked to potentially serious or life-threatening complications. Our research will limit the potential for complications even further by screening and excluding patients with a known allergy to materials of porcine origin. Lastly, the ECM grafts are FDA-approved scaffold material that is indicated for reinforcement or augmentation of soft tissue repairs. In view of this, we will not be deviating from the standard of care by using the ECM allograft and the investigators do not anticipate having to discontinue the study or having to alter the protocol based on interim results. For these reasons, an independent data monitoring committee will not be needed or used.

9. Consent

In a private, outpatient setting, the PI or one of the research coordinators involved in the study will describe in detail the characteristics of the research study. Understandable language will be used. The process of pre-operative assessment, randomization, treatment, data collection and analysis along with the potential risks/benefits of the study are to be described in detail. Furthermore, the methods of maintaining data security and confidentiality will be outlined. The patient is to be explicitly told that he or she does not have to participate in the study and that regardless of his/her decision, will receive the best care this hospital can provide.

The informed consent process will take place during the patient's pre-operative clinical visit. The original consent form will be kept with study records by the principal investigator in a secure location, and a copy of the consent will be given to the subject. The subject's decision to participate will be documented in his or hers electronic record. A copy of the consent may be placed in the hospital record.

10. Principal Investigators

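### The arm is fixed on the consent day, but reparability and the need to augment a control are settled at surgery, and the plan then removes those patients from the randomised comparison

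*Combined protocol and SAP*

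**What the plan says.** **Timing of allocation.** Section 2.C (Randomization): "All patients that meet the criteria will be randomized the day the informed consent is signed". Section 9 (Consent) gives the usual time: "The informed consent process will take place during the patient's pre-operative clinical visit". Section 2.A allows an exception after documented telephone contact: "Patient will be consented in-person on same-day as surgery, only if the above is completed and documented". Section 6 (Labeling) calls the study open-label. No section describes allocation concealment or says when the surgeon learns the arm.

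**What is settled at surgery.**
- Reparability. Section 2.D.3 (Alternative Treatment Group) covers patients "where a repair cannot be accomplished due to intraoperative findings will remain in the study". They are analysed separately.
- Augmentation of controls. Section 5 expects fewer controls to complete because "augmentation may be required due to tear severity and other procedure variables". Those controls are withdrawn, and safety follow-up is optional.
- Tear size, in some cases. Section 1.A: "The cuff tear size will be determined on either pre-operative magnetic resonance imaging (MRI), or ultrasound (US), or intra-operative measurements", with CT as a fourth source.

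**Analysis sets.** Section 5 limits the intent-to-treat population to subjects with completed repair surgery, and the per-protocol population to those who completed every visit without a major violation.

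**The concern.** Randomisation makes the arms comparable at the moment of allocation. Here that moment usually precedes the operation, and at the operation patients can leave the comparison for reasons tied to how bad the tear is. The plan describes a severity-driven exit from the control arm and none from the graft arm, where a severe tear receives the graft and stays in. Because the study is open-label, whoever decides that a control needs augmentation can know that the patient is a control.

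Tear severity plausibly predicts re-tear, which is the primary outcome. Removing the more severe controls makes the remaining control arm look better than the arm that was randomised, so the comparison shifts against the graft. Covariate adjustment is planned only as a secondary analysis, and adjusting for recorded severity could not be relied on to repair a selection made on the surgeon's overall judgement.

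**Working it through.** **1. Order of events.**

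| Step | When | Source |
|---|---|---|
| Consent | Pre-operative visit; exceptionally the day of surgery | Sections 9, 2.A |
| Randomisation | Same day as consent | Section 2.C |
| Tear size, retraction and tissue quality recorded | At surgery, before repair | Section 2.E |
| Tear found not repairable | At surgery | Section 2.D.3 |
| Control augmented, then withdrawn | At surgery | Section 5 |

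On the usual route, the last three steps follow allocation. Same-day consent does not rule out randomising in theatre, but nothing requires it.

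**2. What each analysis set does with these patients.**
- Unrepaired patients fall outside the intent-to-treat set by its definition, and Section 2.D.3 analyses them apart.
- Augmented controls have had a repair, so they could meet the literal intent-to-treat wording. But Section 5 withdraws them with at most safety follow-up, so no 1-year MRI is assured, and nothing says they are analysed as controls.
- Withdrawn patients do not complete all visits, so they also leave the per-protocol set.

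Neither set is all patients as randomised.

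**3. Size of the selection effect.** The documents give no crossover share and no re-tear risk for such patients, so both are assumed. Let x be the share of controls withdrawn, r the re-tear risk they would have had as controls, and 40% the control re-tear rate (Section 5). The rate among remaining controls is

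(0.40 − x·r) / (1 − x).

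Suppose the graft has no effect, so the graft arm also runs at 40%. With x = 0.20 and r = 0.60:

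(0.40 − 0.12) / 0.80 = 0.28 / 0.80 = 35%.

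In patients: 7 of 35 controls leave, taking 4.2 of the 14 expected re-tears, and 9.8 / 28 = 35%. The arms show 35% against 40%, a spurious 5 points against the graft.

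Remaining control rate over a range of assumptions (true rate 40%):

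| Withdrawn (x) | r = 50% | r = 60% | r = 80% |
|---|---|---|---|
| 10% | 38.9% | 37.8% | 35.6% |
| 20% | 37.5% | 35.0% | 30.0% |
| 30% | 35.7% | 31.4% | 22.9% |
| 40% | 33.3% | 26.7% | 13.3% |

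If r = 40%, so that withdrawal is unrelated to risk, the remaining rate is 40% for every x. The bias comes from the link with severity, not from the smaller number.

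**The case against.** **Eligibility is a pre-operative item.** The Schedule of Activities places it at screening, Section 2.A identifies patients already scheduled for repair of a tear of at least 2.5 cm, and Section 3.A lists eligibility and shoulder imaging before surgery. Intra-operative measurement is one of four size sources. This stands. A reader might infer that eligibility generally fails after allocation. The documents do not support that: no section removes a randomised patient whose tear measures below 2.5 cm. What remains is narrower. The intra-operative option does not fit randomisation on the consent day, and there is no rule for a measurement that disagrees with imaging.

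**Differential loss is documented only for augmented controls.** This also stands. Irreparable tears can occur in either arm, and Section 2.D.3 states no imbalance.

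**Baseline surveys.** A reader might infer from "After enrollment, all indicated preoperative assessments will be performed and recorded" that surveys are completed with knowledge of the arm. That sentence is in Section 2.B, ahead of the randomisation section, and the surveys belong to the screening visit. The order is not fixed explicitly, but nothing places the surveys after allocation.

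**Timing need not change.** Analysing everyone as randomised would by itself protect the comparison. That is true, but each crossover would then dilute the contrast. Late allocation prevents most crossovers from arising, so the two changes work best together.

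**Conclusion.** The concern holds for patients found unrepairable and for controls augmented after allocation, and as an ambiguity for tear size. Followed as written, the plan removes severe controls selectively from an open-label comparison, and neither analysis set restores them. The direction of the bias, against the graft, rests on augmented controls having an above-average re-tear risk, which the plan's reference to tear severity makes likely but does not quantify. The 5-point figure is an illustration. Over 10–40% withdrawn and 50–80% re-tear risk, the spurious difference runs from about 1 point (40 − 38.9) to about 27 points (40 − 13.3), with the upper end an extreme case.

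A reader might take the 40% and 20% used in Section 5 to inflate the sample as attrition rates, and derive a crossover share from their difference. They are the assumed re-tear rates, so they support no such share.

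Nor does the fix restore power. With no crossover at all, 35 per arm gives about 45% power for 40% against 20% (two-sided 5%, pooled z test). If the same severe patients (20%, with re-tear risk of 50–70%) are excluded before allocation, control risk is 37.5–32.5%. Power at 35 per arm is then about 42–35% if the graft still halves the risk. Low power is a separate sample-size matter.

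**What to change.** 1. Keep consent as it is. In Section 2.C, generate or reveal the allocation in the operating room, only after the tear has been measured and meets the size criterion, reparability has been recorded, and the surgeon has recorded willingness to follow either allocation. Section 2.E already records tear size, retraction and tissue quality before repair; reparability and willingness would be added. REDCap, already the study database, or sealed envelopes could deliver the allocation.
2. Log patients who fail at that point as not randomised, with the reason. For most of them this replaces the Alternative Treatment Group and the withdrawn-control category.
3. In Section 5, define the primary intent-to-treat set as all randomised patients in their assigned arm, including any later crossover, and follow all of them to the 1-year MRI.
4. State which size measurement governs eligibility when imaging and intra-operative measurement disagree.

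**Cost.** A protocol amendment and an allocation step in theatre. A graft must be on hand for every consented case; Section 6 says it is stored at room temperature. Patients will not know their arm before surgery. Some severe tears may be excluded before randomisation, which narrows applicability in a trial of large and massive tears and slows recruitment.

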A power analysis was also considered for shoulder function, a secondary clinical outcome. It demonstrated that at least thirty-four cases must complete the study (seventeen cases in each arm- augmented and control) in order to assess the difference between each group. This sample size was statistically derived by an ASES score power analysis, using a power of 0.8, an effect size d of 0.9, an alpha error probability of 0.05, and an allocation ratio of 1. This is assuming an ASES score of 84 at 12 months postsurgical repair in the augmented group (standard deviation of 16) and 72 (standard deviation of 12) for the control group. The ASES data used was derived from a recently completed ArthroFlex rotator cuff repair study for which data is on file at LifeNet Health. Again, with the assumption that the control group will have a failure rate of approximately 40% and the augmented group will have a failure rate of approximately 20%, at least 30 should be randomized in the control group and 22 in the augmented group to assess a difference in shoulder function.

Once data is acquired for 15 subjects in each group, a post-hoc power analysis will be conducted to confirm that alpha and beta error probabilities are still under the accepted limits.

The primary analysis will be conducted on both the intent to treat and the per protocol populations. The intent to treat population will be comprised of all subjects that have completed rotator cuff repair surgery. The per protocol population will be comprised of all subjects that have completed all study visits and did not have any major protocol violations (e.g., missed visits, noncompliance with postsurgical instructions, etc.). Standard adjustments to analyses for pre-specified or baseline-suggested clinical covariates will be made; these covariate-adjusted analyses will be considered secondary analyses. Primary analysis results will be declared statistically significant if the two-sided p-value is less than 0.05.

Safety analyses will be performed on the intent to treat population and will include the incidence of treatment-emergent AEs and clinically significant changes in vital signs and

physical examinations. Impact of treatment on infection rate, treatment emergent AEs, and changes in vital signs and physical examination will all be assessed.

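### The sample size assumes 40% vs 20% re-tear with no allowance for controls who receive the graft, and Section 5 both withdraws those patients and counts them as intent-to-treat

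*Combined protocol and SAP*

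**What the plan says.** All of the following is in Section 5 (Sample Size Justification and Statistical Analysis) unless noted.

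- The source of the control rate: "A re-tear rate of 40% is expected in patients who have undergone rotator cuff repair for large and massive rotator cuff tears". It is a literature figure for such repairs as a whole, with no selection on severity stated.
- The graft is expected to cut this by "approximately half (~20" per cent), while "the control group would experience rates of re-tear comparable to what is reported in the current literature (~40" per cent).
- The size: "Power analysis indicated that 20 patients in each group would provide sufficient power to identify statistical significance in healing rates". No numerical power is given for this outcome. Then, citing the two assumed failure rates, "at least 34 should be randomized in the control group and 26 in the augmented group".
- Crossover: fewer controls are expected to complete because "augmentation may be required due to tear severity and other procedure variables". These controls are described as withdrawn, with safety follow-up optional.
- Analysis sets: the primary analysis uses both an intent-to-treat and a per-protocol population. "The intent to treat population will be comprised of all subjects that have completed rotator cuff repair surgery". The per-protocol set requires all visits and no major violation. Crossover is not among the examples of a violation, and the arm in which a crossed-over control is analysed is not stated.
- Section 1 and the Synopsis now randomise 70 patients, 35 to each arm. Section 2.D.1 says that controls receive no ECM graft.

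**The concern.** The planned 20-point difference compares controls who all go without the graft with patients who all receive it. Section 5 itself expects that some controls will not go without it, and that tear severity is one of the reasons. The plan treats this as a matter of how many controls complete. It leaves the 40% and 20% unchanged.

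Two things follow. First, Section 5 gives two incompatible fates to the same patient: withdrawn under the sample-size paragraph, included under the intent-to-treat definition. Second, under either fate the contrast being analysed can differ from the one used for sizing. Extra controls would replace missing completers, but they do not restore a diluted difference or undo a selected control arm.

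At stake is how the result is read. If power is later restated with a proper calculation for proportions but still at 40% vs 20%, it will remain too high for the analysis actually done. A non-significant result could then be taken as evidence that the graft does not halve re-tears, when the trial never made that comparison cleanly.

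**Working it through.** **Inputs from the documents.** Control rate 40%; graft rate 20%; two-sided alpha 0.05; 35 per arm. **Assumptions, because the documents give no figure.** c = share of controls who receive the graft; r = the re-tear risk those patients would have had without it; complete 1-year MRI in everyone analysed.

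**The plan's own figures.** The 20 per group does not reproduce as a comparison of 40% with 20%. The usual two-proportion formula gives 82 per arm for 80% power (a level the plan states only for the ASES calculation), and 20 per group gives about 28% power. The SD in the text ("An SD of 15% within groups was allowed") is not a parameter of such a comparison. The step to 34 and 26 does follow from the re-tear rates used as attrition: 20/0.6 = 33.3, so 34; 20/0.8 = 25, against a stated 26.

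**Baseline power.** Exact enumeration of the Pearson (pooled z) test, 35 vs 35, 40% vs 20%: 45.3%. Fisher's exact test gives 35.7%.

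**Case A: augmented controls analysed as randomised.** If they re-tear at rate g once grafted, the control-arm rate is 0.40 − c × (r − g).

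- No severity selection: r = 40%, g = 20%, so the rate is 0.40 − 0.20c.
- Severity selection: r = 60%, halved by the graft to g = 30%, so the rate is 0.40 − 0.30c.

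| c | Control rate, no selection | Power | Control rate, r = 60% | Power |
|---|---|---|---|---|
| 10% | 38% | 38.4% | 37% | 35.1% |
| 20% | 36% | 31.8% | 34% | 25.7% |
| 30% | 34% | 25.7% | 31% | 17.8% |

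The loss from 45.3% runs from 6.9 points (45.3 − 38.4) to 27.5 points (45.3 − 17.8). At c = 5% without selection the control rate is 39% and power 41.9%, a loss of 3.4 points.

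**Case B: augmented controls removed.** The remaining controls re-tear at (0.40 − c × r)/(1 − c). With c = 20% and r = 60%: (0.40 − 0.12)/0.80 = 35%. The comparison is 28 controls at 35% against 35 graft patients at 20%, and exact power is 31.4% (26.8% by normal approximation; the exact figure is affected by discreteness at these sizes). With r = 40% the formula returns 40%: without severity selection, removal does not move the control rate.

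**Does severity raise the risk?** The Introduction attributes repair failure to tension at the repair and tendon quality, among other factors. That supports r above 40% in direction but gives no value.

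**The case against.** The strongest reply is that the size of the effect is wholly assumed. Neither c nor r is printed, 10% crossover without selection moves the control rate only to 38%, which is within the plan's approximate 40%, and power is already poor before any crossover. All of that stands. It limits how precisely the loss can be stated, and it makes crossover an addition to the main shortfall, not its cause. It does not answer the contradiction over who is analysed, or the absence of any adjustment to the assumed difference.

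Four stronger readings are tempting, and the documents do not support them.

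- A reader might infer that the control rate must fall below 40% in both primary populations. Removal lowers it only if severer tears re-tear more often, which the Introduction supports qualitatively. Section 5 also names other procedure variables besides severity.
- A reader might take the step from 34 randomised to 20 completing controls as an estimate of crossover (14/34). It is not one: 34 is 20 divided by 0.6, the re-tear rate used as attrition.
- A reader might say the plan claims that randomising more controls covers these patients. No sentence says so. The 34 and 26 are tied to the failure rates, and the current 35:35 allocation no longer favours controls.
- A reader might correct the control rate by the single formula 40% minus 20 points times c. That assumes no severity selection, so it is only the mild end of the range.

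**Conclusion.** The point holds as a flaw in a design assumption and in the definition of the analysis sets. The 40% vs 20% contrast is carried into the sample size unadjusted although the plan expects crossover to the graft, and Section 5 both withdraws and includes the patients concerned.

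If they are analysed as randomised, the difference shrinks whenever the graft helps them at all, which is the plan's own premise. If they are removed, it shrinks on condition that severity raises re-tear risk. For c between 10% and 30%, power at 35 per arm falls from 45% to between 38% and 18% when they are analysed as randomised. In the one removal case worked here (c = 20%, r = 60%) it is 31%. These figures rest on assumed c and r, and on the premise that the graft halves risk. Direction is well supported; magnitude is not known.

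**What to change.** 1. In Section 5, state an assumed crossover share c, separately from loss to follow-up. Give the resulting intent-to-treat difference and the achieved power at 35 per arm as a range over c and over the ungrafted risk of the augmented controls (the table above would serve), not as one formula.
2. Reconcile the withdrawal sentence with the intent-to-treat definition. Augmented controls should stay in the intent-to-treat analysis in their randomised arm, with the already scheduled 1-year MRI as their outcome, instead of being withdrawn with optional safety follow-up. Section 2.D.1 and Section 5 should also be made consistent on whether a control may receive a graft; that is a clinical matter on which this review takes no position.
3. Optionally, add a complier-average estimate, with assigned arm as the instrument, as a supplementary analysis. Say that it will be imprecise at this size and that it depends on the MRI in item 2.

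The cost is a less favourable stated power, some redrafting, and completion of the scheduled follow-up in what should be a small number of augmented controls. No patients are added.
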